1. INTRODUCTION

Hemodialysis is the most common treatment in the end stage renal disease. In the 2018 report of the World Health Organization, it was stated that 2.62 million people received dialysis treatment in 2010 and 1.2 million people died from kidney disease in 2015 (Luyckx, Tonelli, & Stanifer, 2018). Hemodialysis consists of a complex process and adherence to treatment is very important for individuals receiving hemodialysis treatment. Adherence to fluid intake, diet and drug management is indicators of adherence to treatment (Naalweh et al., 2017; Tohme et al., 2017). Non-adherence to treatment leads to increased complications, decreased quality of life (QOL) and increased morbidity and mortality (Naseri-Salahshour, Sajadi, Nikbakht-Nasrabadi, Davodabady, & Fournier, 2020). Therefore improving adherence to treatment is important in hemodialysis.

Motivational interviewing and education are frequently used to improve adherence to treatment and to develop healthy behavior in individuals receiving hemodialysis treatment (Crown, Vogel, & Hurlock-Chorostecki, 2017; Tao, Tao, Wang, & Bi, 2020). Since creating behavioral change is a complex process, it is recommended that the intervention be implemented systematically. Models or theories are important in guiding the interventions and their systematic application (Fawcett, 2005). One of these theories, Jean Watson's Theory of Human Caring dwell on nursing care to be humanistic, conscious, purposeful and careful (Watson, 2018). It is thought that performing of motivational interviewing and education based on Watson's Theory of Human Caring to individuals receiving hemodialysis treatment will contribute to improving adherence to treatment, patient satisfaction and QOL.

This statistical analysis plan (SAP) will give more detailed descriptions of the endpoints in the study and the corresponding analyses.

2. STUDY DESIGN

2.1 Objective and Hypothesis

The aims of the study were to evaluate the effectiveness of Motivational interviewing and education based on Watson's Theory Of Human Caring on adherence to treatment, satisfaction and QOL in individuals receiving hemodialysis treatment. We hypothesized that intervention group who received Motivational interviewing and education based on Watson's Theory of Human Caring would increase (a) adherence to fluid intake, (b) adherence to diet, (c) adherence to drug management, (d) QOL compared to the control group and (e)

intervention group who receiving motivational interviewing and education based on Watson's Theory of Human Caring would satisfied with introduced intervention.

2.2. Design / Methodology

A randomized controlled trial.

2.3. Sample Size Calculation

In this study, the sample size was calculated based on the “The Scale for Dietary Behaviors in Hemodialysis Patients” used in a similar study (Düzalan & Pakyüz, 2018). A total of 70 individuals receiving hemodialysis treatment, 35 patients in each group, were included in the study based on a common type-I error rate of 0.05, the effect size rate of 0.80 and estimated loss to follow-up of 10%.

2.4. Inclusion and Exclusion Criteria

Inclusion criteria of the study were as follows:

- participants were individuals aged ≥ 18 years,
- received hemodialysis for at least 3 months,
- had 1 and over from Diet and Fluid Non-Adherence Questionnaire (DDFQ) total score,
- had 0 or 1 score from 1., 2. and 6. questions or 3., 4. and 5. questions in the Modified Morisky Scale (MMS),
- willing to participate,
- participants without language or communication barriers.

The exclusion criteria of the study were as follows:

- The participants diagnosed with psychiatric illness or malignancy were excluded from the study.

2.5. Randomization and blinding

The simple randomizaton method will used. Individuals receiving hemodialysis who met the inclusion criteria, agreed to participate in the study and signed the informed consent form were divided into either a intervention group or control group by coded randomization by researcher. An independent, blind statistician who will not involved in the research process

prepared the random number table with SAS package 9.4. It will not possible allocation concealment as the intervention was performed by the researcher who received motivational interviewing and education. The researcher will not participate in the data analysis, the analyzes will made by an expert statistician.

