3. ANALYSIS

The data were analysed with the IBM Statistical Package for Social Science (SPSS) for Windows version 25 (IBM, 2017). The normality test was performed with the graphical assessment, skewness and kurtosis test. Descriptive statistics for normally distributed numerical variables were presented as mean, standard deviations, n (%) or minimum-maximum. While evaluating statistical significance, it was considered according to the p value of <0.05 .

Adherence to fluid intake, diet and drug management, physical parameters and quality of life will compare intervention groups (motivational interviewing and education based Watson's Theory of Human Caring vs control treatment) on their mean change between baseline and 12 weeks using independent sample t-test. In addition, effect size will evaluated by calculator for student's t-test using G-Power programme. To identify the relationship of the change adherence to fluid intake, diet and drug management, physical parameters and quality of life with other variables such as group and demographic variables will use multivariate linear regression.

Patiens satisfaction will analyzed using descriptive analysis such as n (%) or minimum-maximum.

References

Düzalan, Ö. B., & Pakyüz, S. Ç. (2018). Educational interventions for improved diet and fluid management in haemodialysis patients: An interventional study. *Journal of Pakistan Medical Association*, 68(4), 532-537.

Fawcett, J. (2005). Watson's Theory of Human Care. In J. Fawcett (Ed.), *Contemporary Nursing Knowledge an Analysis and Evaluation of Nursing Models and Theories* (pp. 553-599). Philadelphia: F.A. Davis Company.

IBM. (2017). SPSS version 25.0. New York: IBM Corporation.

Luyckx, V. A., Tonelli, M., & Stanifer, J. W. (2018). The global burden of kidney disease and the sustainable development goals. *Bulletin of the World Health Organization*, 96(6), 414-422. doi:10.2471%2FBLT.17.206441

Naalweh, K. S., Barakat, M. A., Sweileh, M. W., Al-Jabi, S. W., Sweileh, W. M., & Sa'ed, H. Z. (2017). Treatment adherence and perception in patients on maintenance hemodialysis: A cross-sectional study from Palestine. *BMC Nephrology*, 18(1), 178-186. doi:10.1186/s12882-017-0598-2

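### The researcher who delivers the intervention also allocates patients without concealment, and simple randomisation would give the stated 35 per group only 9.5% of the time

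*Combined protocol and SAP*

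**What the plan says.** Section 2.5 (Randomization and blinding) names the method: "The simple randomizaton method will used". It adds that an independent statistician "prepared the random number table with SAS package 9.4", without saying how the table was built or who held it. Eligible, consenting patients were then "divided into either a intervention group or control group by coded randomization by researcher". The same section says that concealing the allocation is not possible, and gives as the reason that the researcher carries out the intervention. The researcher is kept out of the data analysis.

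Section 2.3 (Sample Size Calculation) states: "A total of 70 individuals receiving hemodialysis treatment, 35 patients in each group, were included in the study". It cites a "common type-I error rate of 0.05", "the effect size rate of 0.80" and "estimated loss to follow-up of 10" per cent.

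Section 3 (Analysis) compares the groups "on their mean change between baseline and 12 weeks using independent sample t-test", with a regression on group and demographic variables as an additional analysis.

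No section mentions blocks, a fixed-total list, strata, or a rule for a group that has filled up.

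**The concern.** Two things do not fit.

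First, simple randomisation in its usual meaning leaves the group sizes to chance, whereas section 2.3 gives them as equal. A reader cannot tell whether 35 per group is a planning figure that will usually be missed, or the product of a restriction that the plan does not describe.

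Second, section 2.5 treats concealment and blinding as the same thing. Concealment means that whoever enrols a patient does not know the next assignment until the patient is irrevocably in the trial. It can be had in an open-label trial. Without it, a researcher who allocates patients and also delivers the motivational interviewing may know the next assignment while judging eligibility. The criteria in section 2.4 leave room for judgement, notably willingness to take part and absence of a communication barrier. If more promising patients are steered to the intervention, the comparison is biased by an amount that no later step in the plan would reveal.

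**Working it through.** **Inputs.** N = 70 and 35 per group (section 2.3); simple randomisation (2.5), with a 1:1 ratio implied by the equal groups; alpha 0.05, effect size 0.80 as worded, and 10% loss (2.3); independent-samples t-test on change (3). Two-sided testing is my assumption.

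**The plan's own figure.** The total of 70 cannot be reproduced uniquely, because neither power nor sidedness is stated. With d = 0.80, two-sided 0.05, and division by 0.90 for loss, the exact t-test needs:
- 80% power: 26 per group, 29 after inflation
- 85% power: 30, then 34
- 90% power: 34, then 38

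None is exactly 35. The point below does not depend on this.

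**Group sizes under simple randomisation.** The size of one group, X, is Binomial(70, 0.5).
- P(35:35) = C(70,35)/2^70 = 0.095, so P(unequal) = 0.905
- P(38:32 or worse) = 0.55
- P(40:30 or worse) = 0.28
- P(43:27 or worse) = 0.072
- Mean absolute difference between groups: 6.7 patients
- 2.5th and 97.5th percentiles of X: 27 and 43

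**Power lost to imbalance.** Noncentral t with 68 degrees of freedom and noncentrality d × sqrt(n1·n2/(n1+n2)), with no loss to follow-up.
- d = 0.80 at 35:35: noncentrality 0.80 × sqrt(17.5) = 3.35; power 91.0%
- d = 0.80 at 43:27: noncentrality 0.80 × sqrt(16.59) = 3.26; power 89.5%, a loss of 1.5 points
- d = 0.80 averaged over the binomial: 90.6%, a loss of 0.4 points
- If 0.80 was meant as the power, the detectable effect at 35:35 is d = 0.68. Average power is then 79.4% against 80.0%, and 77.9% at 43:27.
- With 62 completers at d = 0.80: 87.3% when equal, 86.7% on average

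The t-test remains valid with unequal groups, so imbalance alone is a minor cost.

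**The concealment statement.** Delivering the intervention reveals a patient's group after assignment. Concealment concerns only the time before it. The stated reason therefore supports the claim that the researcher cannot be blinded, but not the claim that concealment is impossible. The plan already has a person outside the research process who makes the list and could keep it.

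**Would permuted blocks be a better sequence?** Suppose that the list is withheld but the researcher remembers past assignments and always guesses the group that is behind, tossing a coin when the groups are level. Expected correct guesses out of 70:
- Simple, uncapped: 35
- Simple, with a group closed at 35: guesses are at chance until closure and certain afterwards. The mean forced tail is 6.65, so 35 + 6.65/2 = 38.3.
- Fixed list of 35 + 35 in random order: 35 + (2^70/C(70,35) − 1)/2 = 35 + (10.52 − 1)/2 = 39.8
- Random blocks of 4 and 6: 48.4 by simulation. As a check, the excess per block of size 2m is (4^m/C(2m,m) − 1)/2, which is 0.83 for size 4 and 1.10 for size 6. That gives 70 × (2.83 + 4.10)/10 = 48.5.

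This guess does not need the block sizes, so varying or hiding them does not defeat it.

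**The case against.** The strongest reply is that nothing here is shown to be broken. The sample-size section may be giving a planning target. An equal split is also the single most likely result of simple randomisation, so it would be wrong to say that the method cannot deliver it. The table may have been a fixed 35 + 35 list loosely called simple. Imbalance costs almost nothing, and where one person sees every assignment, uncapped simple randomisation is the least predictable sequence available. All of this stands. It reduces the sequence issue to a missing description, and it rules out requiring blocks. Something still needs correcting: a fixed-total list is not simple randomisation, and a target should be called a target.

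A reader might also infer that the researcher closed a group once it reached 35, which would leave a tail of forced allocations (mean 6.7, median 6, ten or more in about 25% of trials). The documents describe no such rule. Under a fixed list the final same-group run averages only 1.9. Those figures are therefore not an expected harm of this trial.

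On concealment, it can be said that section 2.5 puts consent before allocation, that a blind statistician made the table, and that the researcher stays out of the analysis. None of these closes the gap. Consent first does not help if the next assignment is already known when the patient is approached, and the plan does not say who held the table. The regression with demographic variables adjusts only for what is measured.

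**Conclusion.** The point holds in a limited form. Read as written, section 2.5 gives the group sizes of section 2.3 with probability 9.5%, and the two sections need a linking statement. This is a defect of description with little statistical cost: about 0.4 points of power on average and 1.5 points at 43:27, assuming d = 0.80, a two-sided 0.05 test and full follow-up.

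The more serious part is unconcealed allocation by the researcher who delivers the intervention, justified by a reason that bears only on blinding. Its size cannot be calculated from the documents: they do not show that the researcher saw the table, or that any patient was selected on that basis. What they show is an open route to selection bias that the primary t-test would not correct and that the trial could close with people already involved. This assumes that the researcher in the allocation sentence and the one in the concealment sentence are the same person, which is the natural reading.

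**What to change.** In section 2.5:

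1. State that the independent statistician keeps the list from the researcher. Each assignment is released singly, or by sequentially numbered opaque sealed envelopes, only after eligibility is confirmed, consent is signed and baseline measurements are recorded.
2. Replace the statement that concealment is not possible with one saying that the researcher cannot be blinded after assignment.
3. Settle the group sizes. Either keep simple randomisation and describe 35 per group in section 2.3 as an expected size, or name the restriction actually used, for example a fixed 35 + 35 list. Small permuted blocks should not be made a requirement, since they raise the expected number of correct guesses from 35 to about 48 of 70 when past assignments are visible.

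The document mixes past and future tense. If allocation is already complete, report how the list was built, who held it and when assignments were revealed, and give the absence of concealment, if confirmed, as a limitation.

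The cost is a few sentences, plus the need for the statistician or the envelopes to be available at each enrolment. Sample size and analysis do not change.

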2.6. Outcomes

This section will present the outcomes investigated to answer the study aims and objectives. The analyses are described in section 3 Analyses.

- Adherence to fluid intake: it will be measured at baseline and 12th week using Fluid Control in Hemodialysis Patients Scale.
- Adherence to diet: it will be measured at baseline and 12th week using The Scale for Dietary Behaviors in Hemodialysis Patients.
- Adherence to drug management: it will be measured at baseline and 12th week using Modified Morisky Scale.
- Patient satisfaction: it will be measured at 12th week in the intervention group using Watson Caritas Patient Score and Motivational Interviewing Evaluation Form.
- Quality of life: it will be measured at baseline and 12th week using Kidney Disease Quality of Life-36 Scale.
- Physical parameter: it will be measured at baseline and 12th week.

Physical Parameters

- Blood Pressure
- BMI
- Glucose mg/dL
- BUN mg/dL
- Creatinine mg/dL
- Albumin g/dL
- Potassium mEq/L

- Phosphorus mEq/L
- Hematocrit %
- Hemoglobin g/dL
- Total Protein mg/dL
- Sodium mEq/L
- Calcium mEq/L

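### Section 2.5 rules out allocation concealment for a reason that bears only on blinding, and does not say who holds the random list or when assignments are released

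*Combined protocol and SAP*

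**What the plan says.** Section 2.5 (Randomization and blinding) gives the method in one sentence: "The simple randomizaton method will used". An independent, blind statistician from outside the research process prepared the random number table in SAS 9.4. Patients who met the inclusion criteria, "agreed to participate in the study and signed the informed consent form", then "were divided into either a intervention group or control group by coded randomization by researcher". On concealment the section says: "It will not possible allocation concealment as the intervention was performed by the researcher who received motivational interviewing and education". It adds that the researcher takes no part in the data analysis.

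Three other sections bear on the point:
- Section 2.4 (Inclusion and Exclusion Criteria) requires willingness to take part and "participants without language or communication barriers".
- The Outcomes section sets the timing of each scale. For fluid adherence, for example, "it will be measured at baseline and 12th week using Fluid Control in Hemodialysis Patients Scale".
- Section 3 (Analysis) compares the groups "on their mean change between baseline and 12 weeks using independent sample t-test" and adds a regression on group and demographic variables.

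**The concern.** Concealment and blinding protect against different things. Concealment keeps the next assignment unknown until the patient has been irrevocably entered. Blinding keeps the assignment unknown afterwards. Who delivers the motivational interviewing matters only after assignment, so the stated reason supports a lack of blinding and nothing more.

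As printed, the plan gives up a safeguard it could have, and makes the person who delivers the intervention also the person who assigns patients. If whoever enrols can see the next code, it can influence who is approached, who is judged to have a communication barrier and how hard consent is pursued. The groups could then differ in motivation, and so in expected change, before any treatment. The change-score comparison and the regression may remove part of a measured imbalance. They cannot remove a difference in unmeasured motivation that predicts change.

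**Working it through.** **What the document settles and what it leaves open**

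| Question | Answer in the document |
|---|---|
| Who generates the list? | An independent statistician (section 2.5) |
| Who assigns patients? | The researcher, by a coded procedure that is not explained (2.5) |
| Who delivers the intervention? | The researcher (2.5) |
| Is consent before assignment? | Yes, by the order in which the steps are listed (2.5) |
| Can the next assignment be guessed from earlier ones? | No, because randomization is simple (2.5) |
| Who holds the list after it is made? | Not stated |
| When does the researcher see the next code? | Not stated |
| Who screens and takes consent? | Not stated |
| Are all baseline outcomes measured before assignment? | Not stated |

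The remaining risk therefore depends on advance access to the table. Listing consent first does not show that the code was unknown when eligibility and willingness were settled. Simple randomization stops guessing, but not reading a table in hand.

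**How much selection could matter**

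The plan gives no figure for this, so the calculation below rests on assumptions.

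Inputs from the document: 35 per group and 10% loss to follow-up (section 2.3), and alpha 0.05 with an independent-samples t-test (section 3). The test is taken as two-sided. Completers per arm: 35 × 0.90 = 31.5, taken as 31. There is assumed to be no true treatment effect.

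*Step 1: a given shift.* Let selection create a difference of d standard deviations in the change score. The rejection rate follows a noncentral t distribution with 60 degrees of freedom and noncentrality d × √(31/2) = d × 3.937.

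| Assumed d | Noncentrality | False-positive rate |
|---|---|---|
| 0 | 0 | 5.0% |
| 0.05 | 0.197 | 5.4% |
| 0.1 | 0.394 | 6.7% |
| 0.2 | 0.787 | 12.1% |
| 0.3 | 1.181 | 21.3% |

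*Step 2: enrolment behaviour that could produce such shifts.* Let motivation be standard normal and correlate r with the change score. Candidates below the median are skipped with probability q when the next slot is intervention. The expected shift is r × 0.798 × q/(2 − q). For q = 0.5 and r = 0.3 this is 0.3 × 0.798 × 0.5/1.5 = 0.080. If above-median candidates are also skipped for control slots with the same q, the shift doubles. Rejection rates come from 40,000 simulated trials per case.

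| Behaviour | Shift (r = 0.3 / 0.5) | False-positive rate (r = 0.3 / 0.5) |
|---|---|---|
| Skip a quarter of low-motivation candidates, intervention slots | 0.034 / 0.057 | 5.2% / 5.7% |
| Skip half, intervention slots | 0.080 / 0.133 | 6.1% / 8.1% |
| Skip half, both arms | 0.160 / 0.266 | 9.5% / 18.0% |

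A repeat of the simulation agreed within about half a percentage point. The values of d, q and r are assumptions; the document gives none of them.

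**The case against.** The strongest reply is that the sentence is a wording slip. The section heading pairs randomization with blinding, the reason given fits blinding, and the English is uneven throughout. That may well be so. The sentence is then still wrong as printed, and the concealment procedure is still missing.

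Other points deserve credit:
- **Independent generation.** The researcher did not create the sequence. This is a real safeguard, but it does not control access to the list at enrolment.
- **Baseline order.** Modified Morisky Scale scores are an inclusion criterion, so that scale is administered at least once before assignment. Whether that administration serves as the baseline value is not stated, and the other outcome scales remain unordered.
- **Narrow route to bias.** Most entry criteria are objective or scored, and willingness is on its face the patient's decision. The coded procedure may have masked the table. Skipping candidates also needs a surplus of them, and no pool size is given. These points make large bias less likely, but they do not exclude it.
- **Figures.** The mild scenarios stay close to 5%, and the large ones need deliberate steering. The figures show how the test responds to selection; they are not evidence that selection occurred in this trial.

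**Conclusion.** The concern holds. Two things are certain from the text: the reason given does not support the conclusion about concealment, and custody of the list and timing of release are not described. Whether any bias follows cannot be determined. Under the assumptions above, the false-positive rate runs from essentially nominal (5.2% with mild skipping and r = 0.3) to 18.0% with steering in both arms and r = 0.5, or 21.3% for an assumed shift of 0.3 SD. The case for correction rests on the wording and the missing mechanism, not on these rates. A reader of the plan has no basis for ruling selection out.

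**What to change.** The first step depends on whether enrolment has happened. The document mixes tenses; section 2.3, for instance, says "35 patients in each group, were included in the study".

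**If enrolment is complete:** state who held the table, what the coding hid, when each assignment became known to the researcher, and whether all baseline measurements came first. Report any lack of concealment as a limitation. Do not claim concealment that was not in place.

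**If enrolment is still to come, in whole or in part:** rewrite section 2.5 so that the independent statistician keeps the list and releases assignments one patient at a time, only after eligibility, consent and all baseline measurements are recorded. Release can be by message or by sequentially numbered, opaque, sealed envelopes that the statistician prepares.

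**In both cases:** replace the sentence on concealment with two separate statements. One should say that participants and the interventionist cannot be blinded. The other should say how allocation was or will be concealed until baseline is complete, or that it was not.

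**Cost:** 2 × 35 = 70 messages or envelopes from a statistician already engaged, some minor logistics and a short delay before the first session. The statistician, now described as outside the research process, would take on a small operational role. Sample size, alpha and power do not change. If enrolment is over, only the reporting can be corrected.
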